### **Near infrared cholangiography (NIR-C)**

NIFC is performed injecting intravenously, 2.5-7.5 mg of indocyanine green (0.2 mg/kg) at the admission of the patients into the hospital, in patients admitted the same day of surgery, and at least 45 mins before the acquisition of the images. Indocyanine green rapidly binds to plasma proteins and is exclusively and entirely excreted by the hepatic parenchymal cells into the bile, starting within a few minutes after injection. During dissection, the fluorescence imaging mode is used when needed until critical view of safety is obtained. Before division of any tubular structure, the fluorescence imaging mode is routinely used again, and fluorescent angiography is performed by re-injecting the same dose of indocyanine green as initially used. After division of the cystic duct and artery, the fluorescence imaging mode is applied again to check for bile leakage. Time consumption includes the period from the initial dissection and the obtaining of an acceptable CVS and transect the cystic duct.

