The CVS, more than a technology the others, is a technique, introduced by Strasberg and Brunt in 1995, [23] and it is considered the gold standard to perform a safe cholecystectomy with identification of biliary structures (eg, cystic duct, common hepatic duct, and common bile duct) during dissection. Three criteria are required to achieve the CVS: (1) the hepatocystic triangle must be cleared of adipose and fibrotic tissues; the common bile duct and common hepatic duct must not be exposed; (2) the lower third of the gallbladder must be separated from the liver bed to expose the cystic plate; and (3) 2 and only 2 structures should be seen entering the gallbladder. In this case, the main drawback for ST is the necessity to dissect around the Calot's triangle to demonstrate the CVS. It can become challenging for an attending surgeon to supervise the resident to dissect and demonstrate CVS without any visual landmarks.

The most recently introduced intraoperative imaging technique is the near-infrared fluorescent cholangiography (NIRF-C), described by Ishizawa et al in 2009. [24] The NIRF-C allows a real-time enhanced visualization of the extrahepatic biliary tree by fluorescence. NIRF-C is based on the administration of a fluorophore, the indocyanine green, which is excreted in the biliary system, and on the use of a nearinfrared light source, exciting the fluorophore and enabling the visualization. NIRF-C offers some clear advantages when compared with the conventional cholangiography (real-time visualization of biliary tree, reduced costs, easy learning curve, lack of X-ray exposure, safer dissection of Calot's triangle, and possibility to associate fluorescent angiography to highlight vessels). [34, 35] Additionally, NIRF-C has shown a good potential as a teaching tool for trainees. [1, 36]

Previous report demonstrated the feasibility and safety of NIRFC [37]. Prospective study comparing IOC and NIRFC, that the latter is associated with a shorter duration of operation [38] and confirmed its non-inferiority to IOC to X-ray cholangiography in visualizing the critical junction during LC. [39]

Unfortunately, however, as confirmed the EURO-FIGS registry on fluorescence-guided surgery, there is a wide disparity in terms of protocols for NIRFC, across several European surgical centers, particularly in terms of ICG dose and timing of administration. [40]

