## **7.2 Inclusion criteria**

- Patient scheduled for elective laparoscopic cholecystectomy
- Patient age  $\geq$  18 years
- Patient able to give consent to the procedure

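### The indocyanine green dose in Section 8 is written as 2.5 to 7.5 mg and as 0.2 mg/kg; the two agree only between 12.5 and 37.5 kg, so they conflict for practically every adult enrolled

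*Protocol*

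**What the plan says.** Section 8 (Near infrared cholangiography) prescribes the first intravenous injection as "2.5-7.5 mg of indocyanine green (0.2 mg/kg" and closes the bracket after the per-kilogram figure. It calls neither figure a cap, a minimum or an alternative to the other, and no other section states a dose. The injection is given at least 45 minutes before imaging.

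Before any tubular structure is divided, the same section requires a second injection: "fluorescent angiography is performed by re-injecting the same dose of indocyanine green as initially used".

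Section 7.2 admits consenting adults, the first criterion being "Patient scheduled for elective laparoscopic cholecystectomy". Neither Section 7.2 nor the exclusions in Section 7.3 limit body weight.

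Section 4 describes existing practice across European centres as widely disparate, "particularly in terms of ICG dose and timing of administration". Section 5.3 says the trial is meant to arrive at one standard technique for cholecystectomy by trainees. Section 6.3, the list of evaluated parameters, includes neither the administered dose, nor the injection time, nor body weight.

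**The concern.** A bracketed per-kilogram figure after a milligram range reads as a conversion of that range. If the conversion fails for the enrolled population, the instruction has two meanings. One centre can work from the milligram range and another from body weight, and both can say that they followed the protocol.

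At stake is what the NIR-C arm consists of. Section 4 presents disparity in dose between centres as a weakness of current practice, and this text allows the same disparity inside one arm of a multicentre study that aims at a standard. Because Section 6.3 lists neither dose nor weight, the parameters as listed could not show afterwards which expression each centre used.

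**Working it through.** **Inputs.** The milligram range is 2.5 to 7.5 mg and the per-kilogram figure is 0.2 mg/kg (both Section 8). The second injection equals the first (Section 8). Patients are 18 or older with no weight limit (Sections 7.2 and 7.3). The documents give no body weights, so 50 to 100 kg is my assumption for ordinary adults, with 40 and 120 kg as extremes.

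**Step 1: weights at which the two expressions agree.** Weight = dose / 0.2 mg/kg.
- Lower end: 2.5 / 0.2 = 12.5 kg
- Upper end: 7.5 / 0.2 = 37.5 kg

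The stated equivalence therefore cannot be reproduced for anyone heavier than 37.5 kg. This step needs no assumption about typical weight.

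**Step 2: size of the conflict.** Dose = 0.2 mg/kg × weight, compared with 7.5 mg, the nearest dose inside the range.

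| Weight (kg) | 0.2 mg/kg gives (mg) | Ratio to 7.5 mg |
|---|---|---|
| 40 | 8 | 1.07 |
| 50 | 10 | 1.33 |
| 70 | 14 | 1.87 |
| 100 | 20 | 2.67 |
| 120 | 24 | 3.20 |

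Conversely, at 70 kg the milligram range is 2.5 / 70 = 0.036 to 7.5 / 70 = 0.107 mg/kg.

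**Step 3: separate the width of the range from the conflict.** The range alone spans 7.5 / 2.5 = 3-fold. At 100 kg, 20 / 2.5 = 8, but this is 3 × 2.67: the range's own width multiplied by the conflict. Only the second factor comes from the contradiction.

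**Step 4: total over two injections.**
- By the milligram range: 2 × 2.5 = 5 mg to 2 × 7.5 = 15 mg
- By weight, 50 to 100 kg: 2 × 0.2 × 50 = 20 mg to 2 × 0.2 × 100 = 40 mg

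**Step 5: readings that might remove the conflict.**
- *0.2 mg/kg as an upper limit.* This is logically consistent, but the text does not say it, and above 37.5 kg the limit would lie above 7.5 mg and never bind.
- *0.2 mg/kg as the total of both injections.* Each would be 0.1 mg/kg, or 7 mg at 70 kg, within the range for weights from 2.5 / 0.1 = 25 kg to 7.5 / 0.1 = 75 kg. But the bracket is attached to the first injection, and patients above 75 kg would still fall outside.

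Neither reading is stated, so neither can be relied on.

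**The case against.** The strongest case on the other side is that variation between centres may be intended. Section 5.1 calls the study observational, Sections 5.5 and 14 say that nothing is done outside usual care, and the IOC procedure in Section 8 leaves part of the technique to each centre's habits. This has some weight: the protocol need not fix one identical dose everywhere. It does not excuse two figures that disagree. Section 1 calls the study interventional, Section 7 has patients treated according to the protocol, and Section 8 prescribes a dose. If variation is intended, the text has to say so, and what was given has to be recorded.

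Some stronger readings may tempt a reader, and the documents do not support them.
- *An 8-fold contradiction.* That figure sets 20 mg against the bottom of the range and so includes the 3-fold spread that the protocol openly permits. Keeping the range would leave that spread in place.
- *Confounding of the NIR-C comparison.* Dose exists only in the NIR-C arm. Differences in dose between centres are heterogeneity of that intervention and do not by themselves confound it with IOC or CVS-WL.
- *A known effect on the endpoint.* Section 4 reports that practice differs in dose and timing. The documents nowhere quantify an effect of dose on time to CVS.
- *Patients being misinformed.* The patient information is not shown, so what patients are told about the dose cannot be judged.
- *The second injection as an error.* It is clearly stated and has a stated purpose. It only carries the ambiguity into a second administration.

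**Conclusion.** The point holds as an internal contradiction: the two dose expressions in Section 8 cannot both be met by any patient above 37.5 kg, unless one of them is a limit that the text does not declare. The contradiction rests only on adults weighing more than 37.5 kg. Its size, 1.33 to 2.67 times the upper end of the range per injection, rests on the assumed 50 to 100 kg.

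The consequence is that the NIR-C intervention is not uniquely defined. How far this would move time to CVS is unknown, and no sample size, power or significance level depends on it. It must still be corrected before centres start, because it is an unclear drug instruction that defines one of the three arms. The statistical consequences alone would not carry that weight.

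**What to change.** The sponsor should reconcile the milligram range and the per-kilogram figure in Section 8 into one consistent statement. If one figure is meant to limit the other, or to cover both injections, the text should say so. Which figure is right is for the clinical team, and no view is taken here.

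As a separate addition, Section 6.3 should list the administered dose in mg for each injection, the time of each injection, and body weight. The NIR-C arm can then be described by what was actually given, including any spread that a retained range would still allow.

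The cost is one line in Section 8 and a few data fields. The sample size is unaffected.

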### **9.3 Expected Duration of Trial**

The trial is expected to run for 6 months (time from first patient recruitment to last patient evaluation). Data analysis will take a maximum of 3 months after this time.

### **11. Ethics & Regulatory Approvals**

The trial will be conducted in compliance with the principles of the Declaration of Helsinki (1996), the principles of GCP and in accordance with all applicable regulatory requirements including but not limited to the Research Governance Framework and the Medicines for Human Use (Clinical Trial) Regulations 2004, as amended in 2006 and any subsequent amendments.

This study protocol will be submitted for local REC review in addition with patient information leaflet and consent form. The protocol/ any amendments will follow the local REC process. The chief investigator shall provide annual REC reports as required and will notify the REC at the end of the study.

If the study is ended prematurely, the Chief Investigator will notify the REC, including the reasons for the premature termination.

### **12. Data Handling**

The Chief Investigator will act as custodian for the trial data. The following guidelines will be strictly adhered to:

All study data will be:

- Stored in line with the Medicines for Human Use (Clinical Trials) Amended Regulations 2006 and the Data Protection Act.
- archived in line with the Medicines for Human Use (Clinical Trials) Amended Regulations 2006 as defined in the Joint Clinical Trials Office Archiving SOP

### **13. Publication Policy**

It is intended that the results of the study will be reported and disseminated at international conferences and in peer-reviewed scientific journals. Two investigators for each of the involved centres will be included in the authors' list.

### **14. Financial Aspects**

The study does not require additional funding as all patients are not undergoing clinical procedures outside of their usual care. No other procedure is being performed that will require additionally funding than that to perform clinical investigation alone or histopathological analysis.

## 16. Appendixes

### 16.1 APPENDIX A Questionnaire on anatomical identification of the bile ducts

#### Critical view of safety- WL (CVS)

1. What is the quality of visualization?

(Very poor) 1 – 2 – 3 – 4 – 5 – 6 – 7 – 8 – 9 – 10 (Excellent)

2. Has the CVS been achieved?

- Yes
- Probably
- Inconclusive

3. Would you transect the cystic duct based on this image?

- Yes
- No

#### Intraoperative cholangiography (IOC)

1. What is the quality of the IOC (grade best image)?

(Very poor) 1 – 2 – 3 – 4 – 5 – 6 – 7 – 8 – 9 – 10 (Excellent)

2. Is the duct that is cannulated the cystic duct?

- Yes
- Probably
- Inconclusive

3. Would you transect the cystic duct based on this image?

- Yes
- No

#### Near infrared cholangiography (NIFC)

1. What is the quality of the NIFC (grade best image)?

(Very poor) 1 – 2 – 3 – 4 – 5 – 6 – 7 – 8 – 9 – 10 (Excellent)

2. Was the junction well visible?

- Yes
- Probably
- Inconclusive

[figure not shown]
3. Would you transect the cystic duct based on this image?

- Yes
- No

*Adapted from Buddingh KT, et al. Documenting correct assessment of biliary anatomy during laparoscopic cholecystectomy. Surgical endoscopy, 2012, 26.1: 79-85.*

### 16.2 APPENDIX B NASA task load index

## 16.4 APPENDIX D Adverse events score

**Table 1** The intraoperative adverse event classification

Grade	Intraoperative adverse event classification	Percentage of adverse events identified from laparoscopic TME case video review pilot (%)	Examples in laparoscopic colorectal surgery
1	Minor error, no damage or corrective action required	60.1	Peritoneal tear; tissue avulsion from excess traction
2	Minor consequential error requiring corrective action but no change in post-operative care	37.1	Bleeding requiring a corrective step (swab/diathermy), wrong plane dissection—identified and corrected, serosal injury
3	Consequential error requiring major corrective action and/or change in post-operative pathway	2.4	Splenic capsule tear; re-do anastomosis; enterotomy, unplanned stoma
4	Life-threatening complication that requires major or immediate corrective action which led to a significant alteration of the post-operative pathway which may include re-operation or intensive care admission	0.1	Visceral injury; major haemorrhage; any complication necessitating ITU admission
5	Major consequential error resulting in death	0	Major vessel injury, air embolus

The five categories cover all observed intraoperative events by basing the grouping of the therapeutic consequences of the event. Illustrative examples for each category are shown. The vast majority of observed adverse events were seen to be grades I and II with fewer serious events identified

## 16.5 APPENDIX E

**Table 2** EAES classification matrix for bile duct injuries

Anatomic level	Anatomical characteristics					Vasculobiliary injury (yes=VBI+) and name of injured vessel (RHA, LHA, CHA, PV, MV); (no = VBI-)	Time of detection			Mechanism	
	Type and extent of injury						Ei (de visu, bile leak, IOC)	Ep	L	Me	ED
	occlusion		division								
	C	P*	C	P*	LS**						
MBD											
1											
2											
3											
4											
5											
6											
NMBD											

[figure not shown]
For each injury, the surgeon fills in the following matrix: (1) single injury (yes/no); (2) multiple injuries (yes/no). Then one matrix is filled in for each injury, as appropriate. For example, an injury made by an energy-driven (ultrasonic) dissector involving the superior biliary confluence with interruption of the right and left hepatic ducts, detected (intraoperatively) during the operation by the presence of bile would be classed as MBD 4 C VBI Ei, ED. The Connor Garden E6 injury is in fact a type 4 with LS: MBD 4 LS

EAES European Association for Endoscopic Surgery, MBD main biliary duct, NMBD nonmain biliary duct (Luschka duct, aberrant duct, accessory duct), level 1 ≥ 2 cm from lower border of superior biliary confluent, level 2 < 2 cm from lower border of superior biliary confluent, level 3 involves the superior biliary confluent but communication right left is preserved, level 4 involves superior biliary confluent but communication right left is interrupted, level 5a right or left hepatic duct, level 5b right sectorial duct but bile duct still in continuity, C complete, P partial, LS loss of substance, Me mechanical, ED energy driven, VBI vasculobiliary involvement, RHA right hepatic artery, LHA left hepatic artery, CHA common hepatic artery, PV portal vein, MV marginal vessels, Ei early intraoperative, Ep early postoperative, L late, OC intraoperative cholangiogram

a Indicate percentage of circumference, if known

b Indicate length, if known

**Table 9.** Our classification, mechanisms of injury, prevention and treatment

Type	Mechanism of injury	Preventive measures	Treatment for early detection	Treatment for late detection
1	Insecure closure of cystic duct Too deep dissection into gallbladder bed	Attention to operative details	Control bile leak with suturing Laparotomy if required Drain subhepatic space	Drain intraperitoneal collection Control sepsis Endoscopic stenting
2	Incision of CBD instead of cystic duct for operative cholangiogram Clipping of CBD but recognised Laceration of cystic duct/CBD junction Diathermy injury to CBD/CHD	Strasberg's critical view of safety Avoid too much traction on gallbladder Careful use of diathermy	Conversion to laparotomy Repair small laceration Place of T tube controversial Drain subhepatic space If tissue necrosis extensive due to diathermy, treat as Type 3	Early diagnosis without stricture Laparotomy, repair, and drainage Late diagnosis with stricture, treat as Type 3
3	CBD mistaken as cystic duct, with CBD/CHD transected or resected Diathermy injury	Strasberg's critical view of safety Avoid dissection too close to CBD	Conversion to laparotomy Trim divided ducts to healthy tissue Close distal stump HJ to proximal stump Drain subhepatic space	Control sepsis first by draining intraperitoneal collection and proximal bile duct Laparotomy and HJ when sepsis controlled
4	Right HD or sectorial duct mistaken for cystic duct	Recognition of biliary anomaly	Right/left hepatic duct biliary-enteric anastomosis	Asymptomatic: follow up Symptomatic: HJ, liver resection if HJ not possible
5	Right hepatic artery mistaken for cystic artery Diathermy or clip injuries to right hepatic artery during haemostasis	Recognition of vascular anomaly Avoid blind use of diathermy and clip	Reconstruction of vessels and bile ducts if technically possible If not technically possible, ligate duct and vessels and wait and treat as late detection	Asymptomatic with liver atrophy: follow up Symptomatic: HJ±liver resection/liver transplant

CBD: common bile duct; CHD: common hepatic duct; HD: hepatic duct; HJ: hepaticojejunostomy.

*Lau WY, Lai EC. Classification of iatrogenic bile duct injury. Hepatobiliary Pancreat Dis Int 007;6:459-463.*
